3.2.4 EXPLORATORY ENDPOINTS

Through subject questionnaires, other variables that may affect study endpoints will be explored such as smoking, dominant hand, sex, medications, and time spent in the sun.

4 STUDY ENROLLMENT AND WITHDRAWAL

4.1 PARTICIPANT INCLUSION CRITERIA

In order to be eligible to participate in this study, an individual must meet all of the following criteria:

- Provision of signed and dated informed consent form
- Stated willingness to comply with all study procedures and availability for the duration of the study
- Male or female, aged >22
- In good general health as evidenced by medical history
- Ecchymosis greater than 1cm on each arm

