I agree to ensure that all staff members involved in the conduct of this study are informed about their obligations in meeting the above commitments.

Principal Investigator: [name]

_Date: ______ Signature

Title:

A Prospective, Randomized, Split-Arm Clinical Study Investigating the Efficacy and Safety of Sciton's Broad Band for the Treatment and Prevention of Senile Purpura

Précis:

There will be ten subjects, 5 older subjects over 65 years of age with at least one ecchymotic lesion on each arm measuring at least one cm, and 5 subjects under 35 years of age. All subjects will be randomized to undergo 4 Sciton Broad Band Light (BBL) treatments on either their left or right arm one week apart. Subjects will fill out questionnaires, have pictures of their lower arms taken, and will be graded and measured by evaluators regarding the number and size of their ecchymoses as well as side effects such as blistering, pain, erythema, and swelling. One day after their 4th treatment, subjects will have biopsies done to be analyzed for changes in histology and gene expression. The subjects will follow up at 30 days after their last treatments for final pictures of their lower arms and evaluations.

Objectives:

Primary Objectives: To assess the efficacy of BBL in improving the appearance of senile purpura

Important Secondary Objectives:

- 1. To assess the safety of a new BBL protocol for treating and preventing senile purpura
- 2. To assess the efficacy of BBL in reducing skin tears
- 3. To assess the efficacy of BBL to improve the histology of the skin
- 4. To assess the efficacy of BBL to increase epidermal thickness
- 5. To assess the efficacy of BBL to change gene expression

Endpoint

Primary Endpoints:

- Mean absolute difference in the BBL treated arms as compared to the non-treated arms of those with senile purpura in the total square area of purpuric lesions from the first treatment to 30 days after the last treatment
- Mean absolute difference in the BBL treated arms as compared to the non-treated arms of those with senile purpura in the number of purpuric lesions from the first treatment to 30 days after the last treatment

Important Secondary Endpoints:

1. Measurement of pain, swelling, blistering, erythema, and all sideeffects immediately after each procedure, as well as 24 hours, 48 hours, and 7 days after the procedure.

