- 2. Mean absolute difference in the number of skin tears at baseline and 30 days after the last treatment
- 3. The changes in collagen and elastin between untreated and treated skin
- 4. Mean absolute difference in the change in epidermal thickness between treated and untreated skin
- 5. Changes in gene expression between treated and untreated skin

Population: Sample size 10

Male and female adults over the age of 21 living in Palm Beach

County Florida.

Number of Sites 1

Study Agent: Sciton's BBL

Study Duration: 51 days

SCHEMATIC OF STUDY DESIGN

Day -30 to 0 Screening

- •Total n=10
- Obtain informed consent
- Screen potential subjects by inclusion and exclusion criteria (Eligibility Questionnaire)

Day 0: Randomization

•Subjects randomized to have BBL on either their left or right

Day 0: Baseline assessments/ Study Intervention

• Baseline Assessments:

Pre-procedure pictures of patient's lower arms taken with a Digital Camera

Baseline assessment and measurement by evaluator

Baseline Medical History and Medication questionnaires completed by all subjects

• Study Intervention #1:

Sciton's BBL done according to purpura protocol on one arm according to randomized assignment

• Post-Procedure Assessments:

Post-procedure questionnaires filled out by all subjects

Day 1: Follow-up assessments

• At Home Follow-up Assessments Questionnaire Regarding Side-Effects

Day 2: Follow-up assessments

• At Home Follow-up Assessments Questionnaire Regarding Side-Effects

Day 7 +/- 2 Days: Follow-up assessments / Study Intervention

Follow-up assessments:

Evaluator assessment and measurement

Pictures taken of subject's lower arms

Subject follow up questionnaires filled out by all subjects

• Study Intervention #2:

Sciton's BBL done a second time on the assigned arm according to protocol settings

• Post-Procedure Assessments:

Day 14 +/- 2 Days: Follow-up assessments / Study Intervention

• Follow-up assessments:

Evaluator assessment and measurement Pictures taken of subject's lower arms

Subject follow up questionnaires filled out by all subjects

• Study Intervention #3:

Sciton's BBL done a third time on the assigned arm according to protocol settings

• Post-Procedure Assessments:

Post-procedure questionnaires filled out by all subjects immediately after treatment

Day 21 +/- 2 Days: Follow-up assessments / Study Intervention

• Follow-up assessments:

Evaluator assessment and measurement

Pictures taken of subject's lower arms

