3 STUDY DESIGN, OBJECTIVES, AND ENDPOINTS

3.1 DESCRIPTION OF THE STUDY DESIGN

- A Prospective, Randomized, Split-Arm Clinical Study
- Single Center
- Study agent: Sciton's BBL
- Study Interventions: BBL Treatment on Day 0, Day 7, and Day 21
- Evaluations on Day 0, Day 7, Day 14, Day 21, Day 22, Day 51.

This will be a prospective, split-arm clinical study in which 5 subjects will be randomized to which arm will be treated with Sciton's BBL.

All subjects will have their arms shaved prior to the procedure and cleaned thoroughly with alcohol. After the procedure a zinc-based sunscreen will be applied to both arms.

Before each of the four treatments and 30 days after the last treatment, the subjects' number and square area of ecchymoses will be measured by an evaluator. Side effects will be measured on Day 0, 1, 2, 7, 14, 21, 22 and 51. Digital photography of subject's arms will be done on day 0, 7, 14, 21, and 51.

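### The protocol contradicts itself on who may be enrolled and how many are randomised; as a lesser point, the synopsis limit on the primary population is not carried into 3.2.2, 8.1 or the SAP

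*Combined protocol and SAP*

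**What the plan says.** **Who is enrolled.** The Précis describes two cohorts of five. The older cohort is over 65 and must have "at least one ecchymotic lesion on each arm measuring at least one cm, and 5 subjects under 35 years of age"; the closing words of that quote are all that is asked of the younger cohort. The Population entry gives "Population: Sample size 10" and describes "Male and female adults over the age of 21 living in Palm Beach" County, with no cohorts. Section 4.1 says an individual must satisfy every listed criterion. These include "Male or female, aged >22" and "Ecchymosis greater than 1cm on each arm", with no cohorts and no exemption. Sections 6.2.1 and 6.2.2 apply the criteria at screening and at baseline.

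**How many are randomised.** The Précis states: "All subjects will be randomized to undergo 4 Sciton Broad Band Light (BBL) treatments". The schematic also gives a total of 10. Section 3.1 describes a "split-arm clinical study in which 5 subjects will be randomized to which arm will be treated".

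**Who is analysed.** The synopsis defines the first primary endpoint in the treated arms "as compared to the non-treated arms of those with senile purpura in the total square area of purpuric lesions", and the second (number of lesions) carries the same limit. Section 3.2.2, section 8.1 and the SAP state the comparison without it. Section 8.3 plans analysis of the endpoints by age, among other variables, but names no primary population. Section 8.4 gives no sample-size calculation because this is a pilot.

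**The concern.** The Précis and 4.1 cannot both be followed. Staff who apply 4.1 must refuse a lesion-free subject under 35, whom the Précis would accept. They may accept a 50-year-old with lesions, who belongs to neither cohort. If they instead enrol the Précis cohort without lesions, each such subject departs from 4.1, and section 10.3 treats any noncompliance with the protocol as a reportable deviation. The count of randomised subjects, five or ten, is open as well.

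The analysis question follows from this. An analyst working only from 3.2.2, 8.1 or the SAP sees no limit to subjects with purpura, so the paired t-test could be run on the purpura subjects or on everyone randomised. If some of those randomised had no lesions on either arm, the two analyses would estimate different quantities.

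**Working it through.** **1. Headcount.** The Précis gives 5 + 5 = 10. This agrees with the Population entry and the schematic, but not with the five randomised in 3.1.

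**2. Eligibility, side by side.**

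| Subject | Précis | 4.1 as written |
|---|---|---|
| Over 65, lesion above 1 cm on each arm | eligible | eligible |
| 35 to 65, lesion above 1 cm on each arm | in neither cohort | eligible |
| Above 22 and under 35, lesion above 1 cm on each arm | eligible | eligible |
| Above 22 and under 35, no lesion | eligible | excluded |

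Rows 2 and 4 conflict. Two smaller mismatches are boundary wording only: above 22 against over 21, and a lesion above 1 cm against one of at least 1 cm.

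**3. Consequence for the primary test.** The plan has no power figure to reproduce; it gives no SD, effect size, alpha or dropout rate. The following are therefore assumptions: alpha 0.05, normal within-subject differences with SD 1 among purpura subjects, and differences of exactly zero in five lesion-free younger subjects.

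Let m and s be the mean and SD of the five purpura differences.

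- Pooled mean: (5m + 5 × 0)/10 = m/2.
- Pooled sum of squares: 4s² + 5(m/2)² + 5(m/2)² = 4s² + 2.5m².
- Five alone: t = m√5/s on 4 df. Critical values are 2.132 one-sided and 2.776 two-sided.
- Pooled: t = (m/2)/√[(4s² + 2.5m²)/90] on 9 df. Critical values are 1.833 and 2.262. As m/s grows, t tends to 0.5/√(2.5/90) = 3.0.

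Power for five alone is from the noncentral t with noncentrality √5 times the standardised effect. Power for the pooled set is from 200,000 simulated trials per effect:

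| Assumed effect (SD) | Two-sided, five alone | Two-sided, pooled | One-sided, five alone | One-sided, pooled |
|---|---|---|---|---|
| 1.0 | 40% | 30% | 58% | 57% |
| 1.5 | 71% | 59% | 86% | 85% |
| 2.0 | 91% | 83% | 98% | 97% |

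**4. If 4.1 is enforced.** All ten subjects have lesions, so there are no structural zeros and the missing limit changes little. If all ten shared the same effect and SD, two-sided power at 1.0 SD would be 80% on 9 df.

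**The case against.** The strongest reply concerns the analysis. The SAP and 8.1 apply the test to the primary endpoint, and the synopsis in the same file defines that endpoint for subjects with senile purpura. Section 8.3 already provides for results by age. The written alternative is also directional, and one-sided power barely moves. This mostly stands: the omission calls for a clarification and is not a second contradiction. It does not remove the need to act, because 8.3 names no primary population and is compatible with a main analysis across all ages.

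A reader might go further and infer that the SAP contradicts the synopsis on who is analysed. The documents do not support that: the later texts are silent on the limit and do not state a different one. Nor do they say that the under-35 subjects are free of purpura, only that no lesion is asked of them.

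On enrolment, one could read the five in 3.1 as the purpura cohort alone. That would still conflict with the Précis, which randomises everyone. Pilot status does not help either. No power calculation is being asked for, and a pilot too must fix who enters and who is analysed.

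**Conclusion.** The enrolment and randomisation texts contradict each other and cannot be followed together: ten randomised against five, and a younger cohort of five that 4.1 would exclude wherever lesions are absent. This rests on the wording alone and must be fixed.

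The missing limit in 3.2.2, 8.1 and the SAP is secondary. It matters only if lesion-free younger subjects are enrolled and pooled. On the zero-difference assumption, the estimated mean difference would then be half that in purpura subjects, and two-sided power would be lower by 8 to 12 percentage points over assumed effects of 1.0 to 2.0 SD.

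A reader might infer that the primary result will be diluted or its interval misleading. The documents do not support that as a prediction. They give no effect size, and they do not say the younger subjects lack lesions. Coverage of the purpura-subject mean by a pooled interval would run from about 79% at 0.5 SD to 31% at 2.5 SD. That range reflects a change in the quantity estimated: at 1.5 SD the pooled interval covers its own mean in about 98% of runs.

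**What to change.** 1. Reconcile the Précis, the Population entry, 3.1 and 4.1 on the number randomised, the age limits, the lesion threshold and the cohort to which the ecchymosis criterion applies. The sponsor decides which eligibility text is right.

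2. Carry the synopsis limit into 3.2.2, 8.1 and the SAP, with the population set by a baseline rule so that a younger subject with lesions has one clear place. For example: *The primary paired analysis includes all randomised subjects who meet the protocol's ecchymosis criterion on both arms at baseline. Randomised subjects who do not meet it are summarised separately and are not pooled in the primary test.* Align 8.3 with this.

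**Cost.** The document carries an IRB approval date, and changing eligibility or the number randomised needs an IRB-approved amendment. No new data or visits are needed, since lesions are already measured at Day 0. If the Précis stands, the primary analysis may rest on about five subjects, fewer after withdrawals (4.4) or data disregarded under 6.3. With five, the 95% interval has a half-width of 2.776/√5 = 1.24 sample SDs. The plan should state this limitation.

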4.2 PARTICIPANT EXCLUSION CRITERIA

An individual who meets any of the following criteria will be excluded from participation in this study:

- Subjects with a history of any arm swelling
- Subjects with allergies to light
- Subjects with auto-immune skin conditions such as lupus, or vitiligo
- Subjects using topical retinol within the last 3 months
- Subjects with any scheduled laser, light, or surgical procedures on the arm during the study
- Subjects unwilling or unable to keep their arms still during digital pictures
- Subjects who are pregnant or nursing
- Subjects with a history of herpes simplex or zoster on their arms
- Subjects with current skin infections, tumors, or dermatitis on the arm
- Subjects with allergies to lidocaine
- Subjects with a history of keloid formation
- Subjects with a history of a bleeding disorder
- Subjects with allergies to adhesives

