Multiple studies have shown the efficacy of topical Retinol and Tretinoin in increasing epidermal thickness and one study in particular in the Journal of Cosmetic Dermatology in 2016 showed not only an increased thickness in the epidermis but also up-regulated genes for Collagen Type 1 (COL1A1) and Collagen Type 3 (COL3A1) with corresponding increases in procollagen 1 and procollagen 3 protein expression (7).

A very small study (N=6) on the effectiveness of human epidermal growth factor for the treatment of actinic purpura when applied twice daily for six weeks showed an increase epidermal thickness on ultrasound and the mean number of lesions decreased from 15 to 2.3 (8).

More recently in 2017, Ceilley published his experience with DerMend in the Journal of Cllinical and Aesthetic Dermatology, reviewing why he thought a topical preparation with Retinol, Alpha hydroxyl acids, Arnica oil, Ceramindes, Niacinamide, and Phytonadione would be an optimal treatment for this condition (3).

The current literature supports the ability of IPL to induce collagen neogenesis. Studies on mice showed that IPL treatments significantly increased the number of collagen and elastic fibers within the dermis and improved the parallel distribution of collagen fibers in relation to the epidermis. These results were only evident after three IPL treatments spaced 2 weeks apart and not after just one or two treatments (5). In a study with rats, IPL increased dermal collagen fibers and collagen fiber diameter after 3 weeks (9) and in another study on rats, IPL increased dermal thickness, density of collagen, the hydroxyproline content, and the expression of III procollagen mRNA (18). In one study in humans, 5 patients showed histological evidence of new collagen formation 6 months after four IPL treatments (19). The current literature not only supports the ability of IPL to induce collagen neogenesis but also microneedling and microneedling with radiofrequency. One study showed microneedling resulted in greater skin and dermal thickness than IPL and increased expression of Type 1 collagen and total collagen content (20).

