In Patrick Bitter's pilot study published in 2015 in the Journal of Cosmetic Dermatology, they used 3'-end sequencing for expression quantification ("3-seq") to discover the gene expression associated with human skin aging and the impact of broadband light (BBL) treatment. In the study skin aging was associated with a significantly altered expression of 2,265 coding and noncoding RNAs, of which 1,293 became "rejuvenated" after BBL treatment (more similar to expression levels in youthful skin). Rejuvenated genes (RGs) included several known key regulators of organismal longevity (16). Hence, according to this study, BBL treatment appears to be able to restore gene expression pattern of photo aged and intrinsically aged human skin to resemble young skin and therefore may be an ideal treatment option for senile or actinic purpura.

In addition, though most cosmetic surgeons and injectors have seen firsthand the improvement of post procedural bruising with both pulse dye lasers or intense pulse light lasers, there are limited published studies on this topic. One study published in the Archives of Plastic Surgery in 2009 showed pulsed-dye laser was effective for treating ecchymoses after facial cosmetic procedures and resulted in a 63% mean improvement in ecchymosis scores within 48 to 72 hours (14), however there are no published studies to date using IPL.

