3.2.2 PRIMARY ENDPOINT

➤ Primary Endpoint: Mean absolute difference between the treated and non-treated arms in the change of total square area and number of ecchymoses from baseline to 30 days after the last treatment.

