4.3 STRATEGIES FOR RECRUITMENT AND RETENTION

- Participants will be compensated by receiving \$5 cash for each visit
- Subjects will receive an email, text or phone call reminder for all their scheduled visits according to their preference
- The source of the subjects will be those who visited Siperstein Dermatology Group and allowed their information to be used in order to be contacted for promotions and trials.

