6.3 PROHIBITED MEDICATIONS, TREATMENTS, AND PROCEDURES

Changes in any anti-coagulants and prednisone use are prohibited during the study as well as any procedures or surgeries on the treatment arm.

In the event a subject makes changes to their medications or has treatments or procedures, the primary investigator will make the final decision regarding early termination from the study or disregarding certain data from final statistical analysis.

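### The laser and light exclusion has no look-back, so a previously light-treated forearm can serve as the untreated reference for the Day 22 biopsy endpoints

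*Combined protocol and SAP*

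**What the plan says.** The only eligibility rule on light-based treatment is in Section 4.2, which excludes "Subjects with any scheduled laser, light, or surgical procedures on the arm during the study". The same list contains a rule that does look back: "Subjects using topical retinol within the last 3 months".

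Section 6.3 governs conduct after entry. Changes in anticoagulant or prednisone use are "prohibited during the study as well as any procedures or surgeries on the treatment arm". It says nothing about the past and does not mention the control arm.

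Section 2.1 describes a human study in which "5 patients showed histological evidence of new collagen formation 6 months after four IPL treatments". It also names microneedling, alone or with radiofrequency, as inducing collagen.

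Section 4.3 recruits from visitors to one dermatology practice who "allowed their information to be used in order to be contacted for promotions and trials".

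The secondary endpoints in Section 3.2.3 compare treated with untreated skin for collagen and elastin, epidermal thickness and gene expression. The schedule in Section 6.2.8 has a single biopsy visit, on Day 22. The primary endpoint in Section 3.2.2 is "Mean absolute difference between the treated and non-treated arms in the change of total square area and number of ecchymoses", measured from baseline.

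**The concern.** A split-arm comparison depends on the control arm being untreated. If that forearm had a light course some weeks before Day 0, it may already carry the tissue change the study sets out to measure.

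The biopsy endpoints are the exposed ones. With one sample per arm after treatment and none before, the control arm is the only reference, and the data cannot separate the study course from an earlier one. Past treatment of one arm goes straight into the between-arm difference. Past treatment of both arms may shrink that difference. A small or null histology or expression result could then mean either that BBL did little or that the reference skin had already been treated.

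The omission also sits oddly with the protocol's own choices. Section 2.1 credits retinol with thicker epidermis and up-regulated collagen genes, and retinol gets a look-back. The study modality, credited there with collagen effects, gets none.

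**Working it through.** **Is the gap closed elsewhere?** The documents state no figure on this point, so the first check is of the text.

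- Section 4.1 (inclusion): nothing on past procedures.
- Section 4.2 (exclusion): future procedures only. If the study is taken to begin with the screening window (Day -30 to 0), the reach is about one month, against the 6 months in Section 2.1.
- Sections 6.1.1, 6.2.1 and 6.2.2: history is taken, but eligibility is judged against the listed criteria, and none concerns earlier light treatment.
- Section 6.3: restricts procedures during the study and names one arm only.
- Sections 3.2.4 and 8.3: earlier light treatment is not among the named exploratory or subgroup variables.

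The gap is not closed.

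**How large could the effect on the biopsy contrast be?** The inputs are assumptions, apart from the number of subjects. Let *T* be the effect of the study course, the same in every subject. Let an earlier course have the same full effect, of which a fraction *p* remains at Day 22. Let *k* of *n* subjects be pre-treated. The Précis has all ten subjects treated and biopsied, while Section 3.1 speaks of 5 subjects being randomised, so both *n* = 5 and *n* = 10 are shown.

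*Both arms pre-treated.*

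- Additive effects: (*pT* + *T*) − *pT* = *T*, so nothing is lost.
- Saturation (the treated arm cannot exceed *T*): *T* − *pT* = (1 − *p*)*T*, so the mean contrast falls by the fraction *kp*/*n*.

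| *k* | *p* | Additive | Saturated, *n* = 5 | Saturated, *n* = 10 |
|---|---|---|---|---|
| 1 | 1 | 0% | 1/5 = 20% | 1/10 = 10% |
| 1 | 0.5 | 0% | 0.5/5 = 10% | 0.5/10 = 5% |
| 2 | 1 | 0% | 2/5 = 40% | 2/10 = 20% |
| 2 | 0.5 | 0% | 1/5 = 20% | 1/10 = 10% |

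*One arm pre-treated, one subject, additive effects.* If the pre-treated arm is the one assigned to BBL, the subject's contrast is (1 + *p*)*T*. If it is the control arm, the contrast is (1 − *p*)*T*. The mean moves by +*p*/*n* or −*p*/*n* of *T*: with *p* = 1, ±20% for *n* = 5 and ±10% for *n* = 10. Random choice of side makes the expected shift zero, but a single such subject always produces one shift or the other.

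**Primary endpoint.** A fixed difference left by earlier treatment is in both the Day 0 and the Day 51 measurements and cancels in the change. What does not cancel is an earlier course still altering bruising between those days.

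**The case against.** The strongest reply is that the consequence is unproven and mostly misses the primary endpoint. Much of this stands.

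- A reader might infer that each pre-treated subject contributes no contrast. That requires saturation as well as full persistence, and the documents do not support saturation. The mouse study in Section 2.1, where a change appeared only after three treatments, points if anything towards accumulation. Zero loss belongs in the range.
- A reader might infer that the primary result is compromised. Change from baseline and randomised side remove most of a fixed carry-over. Entry also requires "Ecchymosis greater than 1cm on each arm", so a subject whose purpura was still fully suppressed by an earlier course would be unlikely to qualify.
- A reader might take the gene-expression study in Section 2.1, with 1,293 of 2,265 RNAs shifted after BBL, as evidence that the effect lasts. It gives no duration. Only the five-patient collagen study bears on persistence, at one time point.
- A reader might infer from Section 4.3 that earlier forearm light treatment is common in this pool. The section does not say so, and Section 2.2 lists no light-based treatment among current options for purpura.
- A reader might convert the shrinkage into lost power. That needs a starting power and a standard deviation, and the plan states neither; Section 8.4 gives no sample size calculation because this is a pilot.

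The eligibility questionnaire is not reproduced and may ask about past procedures. Even so, no stated criterion would act on the answer. None of these replies supplies the missing look-back or a baseline biopsy.

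**Conclusion.** The point holds in a limited form. As written, the criteria admit subjects with recent light treatment of a forearm, and the three biopsy-based secondary endpoints have no protection from it beyond random choice of side, which with 5 to 10 subjects balances one-sided past treatment only in expectation. The primary endpoint is largely protected.

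The size cannot be fixed from the documents. The range of 0% to 20% (or 10% with ten subjects) per subject pre-treated on both arms rests on a common effect and an earlier course equal in strength to the study course; its upper end also needs full persistence and saturation. The count of such subjects is not given and may be zero. The case for correction rests on the gap itself, its inconsistency with the retinol rule and the cited 6-month finding, and the low cost of closing it.

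**What to change.** 1. Extend the Section 4.2 bullet to exclude anyone who has had laser, light, microneedling or microneedling-with-radiofrequency treatment on either forearm within a fixed look-back, as well as anyone with such a procedure or surgery scheduled on either arm during the study. The look-back should be one stated number, longer than 6 months, because the cited human study still found an effect at that point. The sponsor should set the exact length and justify it from its cited persistence data.
2. Put the question, for each forearm, in the eligibility questionnaire and re-check it on Day 0.
3. Reword the procedure restriction in Section 6.3 to cover both arms, consistent with the amended bullet.

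The cost is one amended bullet, one questionnaire line, one wording change and a few more screen failures among practice patients, which should be manageable for a target of ten.
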